9.4.2 ANALYSIS OF THE PRIMARY EFFICACY ENDPOINT(S)

Aim 1.1.

Using the analytical software of APDM, the SWAY and TUG algorithms included in the SAW test will calculate asymmetry and variability for: postural sway (RMS AP & ML planes), cadence (CN), gait cycle duration, gait speed (SN), swing, double support, elevation at midswing, foot strike angle, toe off angle, stance, step duration, stride length (LN), arm swing velocity, arm range of motion, turn angle, turn duration, and turn velocity. All data will be tested for normality with Shapiro-Wilk test. Linear mixed models with repeated measures (LMMRM) will be used to compare high and low frequency over all contact pairs in the levodopa-OFF state. Parameter estimation will be based on restricted maximum likelihood and the form of the covariance matrix will be chosen based on Akaike's Information Criteria and Schwarz' Bayesian Criterion. The Holm-Bonferroni method will be used to adjust for multiple comparisons for the 20 outcome measures.

Aim 1.2. To investigate levodopa's effects on the gait domains, we will include the data for levodopa-ON and add a binary variable for levodopa (on or off) to the LMMRM from Aim1.1.

Aim 2.1. We will utilize the raw data collected during Phase II to develop regression models, under both ON and OFF medication states for all contact pairs. The top panel in Figure 2 presents the overview of Aim 2.1; the goal of this sub-Aim is to predict the gait parameters for patients on low frequency by using the gait sensor measurements obtained on high frequency. Additional independent variables/regressors include general patient/disease characteristics such as age, gender, and disease duration. We will also build models under both ON and OFF medications. To develop the regression models, we use non-linear regression analysis based on random forest (RF) classifier. RF is based on an ensemble of decision trees, referred to as a 'forest,' where predictions for any new observation are obtained from averaging the predictions of individual trees (56). Generally, RF models are not prone to overfitting and are robust against noisy or high-dimensional datasets (57). In addition, they are generally interpretable, allowing for further examination of results and easier subject subtyping with respect to symptomology. However, to assure that the RF based models are the best performing models, we also develop models based on some of the other machine learning techniques, such as neural networks (56), and use them as benchmarks. If needed, to improve model performance we will perform model building in RF models to identify and include the most important parameters (38). We will use techniques such as cross-validation (e.g., leave-one-out) and bootstrapping to examine the generalizability of the models and acquire confidence intervals for the predicted values. Lastly, we will compare the best performing models obtained for both ON and OFF medications and their most important contributing parameters to further investigate the interaction of medications and stimulation frequency.

Aim 2.2. Similar to Aim 2.1, in this sub-Aim we conduct regression analysis to predict gait parameters. However, in this sub-Aim, gait parameters are predicted on low and high frequency in the context of ON and OFF medication conditions using baseline bradykinesia, tremor, and gait sensor measurements, plus MDS-UPDRS III rigidity and axial sub scores. Patient and disease characteristics will be used as regressors. Again, models will be based on RF classifier, where other modeling techniques, such as neural networks, will be used as benchmarks. The best performing parameters identified in Aim 2.1 will be used to guide the model building in this sub-Aim. Also, aforementioned performance enhancing techniques will be used, if possible, and confidence intervals will be generated using bootstrapping. These models will be able to predict the best stimulation frequency and contact pairs for the patient immediately after baseline evaluations and provide a confidence level. Similar to Aim 2.1, we will

develop these models with and without accounting for PD medications to further quantify their impact and provide additional options for patients.

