1 PROTOCOL SUMMARY

1.1 SYNOPSIS

Title: Computational Modeling of 60 Hz Subthalamic Nucleus Deep Brain Stimulation for Gait Disorder in Parkinson's disease

Study Description: The goal of this research is to further our understanding and application of deep brain stimulation in Parkinson's patients with gait disorder.

We will assess the degree to which stimulation parameters affect gait parameters. We will test the hypothesis that the addition of levodopa in combination with stimulation produces a synergistic improvement in certain gait domains. In addition, we test the hypothesis that a subject's gait on stimulation can be predicted with statistically significant accuracy using gait measurements on high frequency stimulation. Finally, we will test the hypothesis that the best stimulation frequency, which yields improvement among various gait parameters, can be predicted using objective sensor data collected at baseline

Objectives:

Aim 1: To determine the impact of 60Hz subthalamic deep brain stimulation on gait kinematics using wearable sensors

- Aim 1.1: To determine whether 60Hz STN-DBS elicits a differential response in gait kinematics compared to high frequency
- Aim 1.2: To determine the influence of 60Hz STN-DBS and levodopa on gait kinematics

Aim 2: To develop machine learning models to predict optimal subthalamic deep brain stimulation frequency based on wearable sensor profiles of baseline Parkinson's motor symptoms

- Aim 2.1: To develop machine learning models to predict gait response to 60Hz stimulation without additional testing
- Aim 2.2: To develop machine learning models to predict best stimulation frequency (60Hz vs. high frequency).

Endpoints:

Primary Endpoints:

Gait parameters:

- Postural sway – root mean square (RMS) sway in antero-posterior (AP) and medio-lateral (ML) planes;
- Gait – cycle duration (seconds), speed (m/s), stance (%), swing (%), heel strike angle (degrees), toe off angle (degrees), stride length (cm), cadence (steps/min), step duration (seconds), elevation at midswing (cm) (foot clearance), double support (%), arm swing velocity (deg/s), and range of motion (degrees);

- Circumduction – turn angle (degrees), turn duration (seconds), and turn velocity (deg/s).

Machine learning models to: 1) predict gait kinematics on 60Hz STN-DBS; 2) predict best stimulation frequency using wearable sensor data collected at baseline.

Secondary Endpoints:

Tremor (rest, kinetic, postural)

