3 OBJECTIVES AND ENDPOINTS

OBJECTIVES	ENDPOINTS	JUSTIFICATION FOR ENDPOINTS
Primary		

Aim 1: To determine the impact of 60Hz subthalamic deep brain stimulation on gait kinematics using wearable sensors
 
Aim 1.1: To determine whether 60Hz STN-DBS elicits a differential response in gait kinematics compared to high frequency
 
Aim 1.2: To determine the influence of 60Hz STN-DBS and levodopa on gait kinematics
	
Postural sway – root mean square (RMS) sway in antero-posterior (AP) and medio-lateral (ML) planes;
 
 • Gait – cycle duration (seconds), speed (m/s), stance (%), swing (%), heel strike angle (degrees), toe off angle (degrees), stride length (cm), cadence (steps/min), step duration (seconds), elevation at midswing (cm) (foot clearance), double support (%), arm swing velocity (deg/s), and range of motion (degrees); • Circumduction – turn angle (degrees), turn duration (seconds), and turn velocity (deg/s). 
Acquired from Opal sensors (APDM, Opal, and Portland, OR)
 
The goal of this sub-Aim is to predict the gait parameters for patients on low frequency by using the gait sensor measurements obtained on high frequency.
 
We will utilize the raw data collected during Phase II to develop regression models, under both ON and OFF medication states for all contact pairs. We will also build models under both ON and OFF medications.
	
Based on normative spatial-temporal gait analysis in healthy young and elderly adults (44-46), we selected the following measurements to be assessed during this instrumented walk

Aim 2: To develop machine learning models to predict optimal subthalamic deep brain stimulation frequency based on wearable sensor profiles of baseline Parkinson's motor symptoms
 
Aim 2.1: To develop machine learning models to predict gait response to 60Hz stimulation without additional testing
		
Random Forest (RF) is based on an ensemble of decision trees, referred to as a 'forest,' where predictions for any new observation are obtained from averaging the predictions of individual trees (56). To develop the regression models, we use non-linear regression analysis based on random forest (RF) classifier. However, to assure that the RF based models are the best performing models, we also develop models based on some of the other machine learning techniques, such as neural networks (56), and use them as benchmarks

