test. During this test, subjects will stand for 30 seconds quietly, then walk 7 meters at their comfortable speed, turn 180 degrees, and walk back. Walking aides will be permissible, if needed. Unless the participant is unable to do so, the SAW test will be conducted twice for each trial in order to capture a sufficient number of gait cycles. Based on normative spatial-temporal gait analysis in healthy young and elderly adults (44-46), we selected the following measurements to be assessed during this instrumented walk: 1) Postural sway – root mean square (RMS) sway in antero-posterior (AP) and medio-lateral (ML) planes; 2) Gait – cycle duration (seconds), speed (m/s), stance (%), swing (%), heel strike angle (degrees), toe off angle (degrees), stride length (cm), cadence (steps/min), step duration (seconds), elevation at midswing (cm) (foot clearance), double support (%), arm swing velocity (deg/s), and range of motion (degrees); 3) Circumduction – turn angle (degrees), turn duration (seconds), and turn velocity (deg/s).

Following the gait testing, participants will undergo tremor and bradykinesia analysis with the Kinesia inertial sensors (Great Lakes Technologies, OH) that will be affixed to their finger and ankle. While seated, subjects will be guided through a series of movement tasks by interacting with the ONE tablet from Kinesia. Each motor test will appear on the touch screen interface that will instruct the participant on the motor task. The following tasks will be performed to assess bradykinesia: finger taps, hand grasps, wrist rotation, toe taps and leg lifts. The tremor assessments will be determined from the following tasks: arms resting (resting tremor), arms extended (postural tremor), and finger to nose (action tremor). Each motor task will last 15 seconds.

Phase II. Participants will be evaluated in two conditions: 1) OFF medication/ON stimulation; 2) ON medication/ON stimulation.

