9.2 SAMPLE SIZE DETERMINATION

To determine the sample size, we averaged the gait parameters (across all age groups) along with pooled variance captured on the APDM inertial sensors for healthy subjects (53) and PD patients with gait disorder (54) and computed a reasonable sample size of 24 (which equates to a Cohen's $d=0.8$) with a power of 0.80 and level of significance of 0.05. Assuming a 20% attrition rate, we will attempt to recruit 30 patients.

Sample Size estimation

$(\alpha) = 0.05, Z_\alpha = 1.96$
 $(\beta) = 0.80$

$$n = \frac{2(Z_a + Z_{1-\beta})^2 \sigma^2}{\Delta^2}$$

Reference Gait values for healthy individuals using APDM sensors

Age Groups	n	mean	STD	Variance
		normalized speed		
20-29	41	1.14	0.12	0.0144
30-39	41	1.16	0.14	0.0196
40-49	42	1.14	0.16	0.0256
50-59	45	1.21	0.14	0.0196
60-69	51	1.13	0.12	0.0144
70-89	72	0.86	0.23	0.0529

Ages 50-89: Mean Velocity - 1.06

Calculated Pooled Variance for Ages 50-89- 0.03

Calculated Pooled Variance for All ages – 0.03

Gait Parameters for PD patients with gait disorder (FOG- & FOG +) using APDM sensors

Walking Measure		Single Task Mean \pm STD
Stride Length (m)	FoG-	1.06 \pm 0.15
	FoG+	0.92 \pm 0.22
Stride Velocity (m/s)	FoG-	0.99 \pm 0.18
	FoG+	0.86 \pm 0.21

Average age 68 STD 8.4 (FOG -)

Average Age 69 STD 7.9 (FOG+)

Mean Velocity – 0.925 (FOG- & FOG+)

de Souza Fortaleza AC, Mancini M, Carlson-Kuhta P, King LA, Nutt JG, Chagas EF, Freitas IFJ, Horak FB. Dual task interference on postural sway, postural transitions and gait in people with Parkinson's disease and freezing of gait. *Gait Posture*. 2017;56:76-81.

Effect Size 1.06-0.925 = .14

$N = 15.79 (.03)/ (.14)^2 = 24 + 20\% \text{ attrition} = \text{total study recruitment } 29 \text{ subjects.}$

Final Study N= 30 subjects

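### Section 9.4.2 does not name the Aim 1 response variable, and the quantities it does name, asymmetry and variability, are not the primary endpoints defined in sections 1.1, 3, 4.1 and 8.1

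*Combined protocol and SAP*

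**What the plan says.** The endpoint sections list values of gait measures, mostly in physical units. Section 1.1 gives, among others, "cycle duration (seconds), speed (m/s), stance (%), swing (%), heel strike angle (degrees), toe off angle (degrees), stride length (cm"). Section 3 repeats the list and ends with "Circumduction – turn angle (degrees), turn duration (seconds), and turn velocity (deg/s"). Sections 4.1 and 8.1 introduce the same set as the measurements taken on the Stand and Walk (SAW) test; in 8.1: "we selected the following measurements to be assessed during this instrumented walk: 1) Postural sway – root mean square (RMS) sway". None of these sections mentions asymmetry or variability.

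Section 9.2 derives the sample size from a difference in mean gait speed: "Effect Size 1.06-0.925 = .14".

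Section 9.4.2, Aim 1.1, is the only text on how these endpoints are analysed. It says "the SWAY and TUG algorithms included in the SAW test will calculate asymmetry and variability for: postural sway (RMS AP & ML planes") and continues through the same parameters. A normality check follows, and then the model: "Linear mixed models with repeated measures (LMMRM) will be used to compare high and low frequency over all contact pairs in the levodopa-OFF state". The multiplicity sentence reads "The Holm-Bonferroni method will be used to adjust for multiple comparisons for the 20 outcome measures". Aim 1.2 reuses this model with a levodopa indicator added.

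On the number of repeats, section 8.1 states: "Unless the participant is unable to do so, the SAW test will be conducted twice for each trial".

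**The concern.** The endpoint sections and the analysis section describe different quantities for the same parameters. Walking speed is a level. Its stride-to-stride spread and its left-right difference are other quantities, and a change in one need not bring a change in the others. Section 9.4.2 names only the latter two and then fits a model with no stated response. An analyst could fit levels, or asymmetry and variability, and claim to have followed the plan in either case.

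At stake is which quantity the primary test concerns. Section 2.1 asks which aspects of gait and balance respond to 60 Hz stimulation and gives speed and stride length as examples, and section 9.2 sizes the study on speed. If 9.4.2 were followed word for word, a change in speed might go untested, or a change in variability might be reported as the primary gait result. Aim 1.2 inherits the same uncertainty.

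**Working it through.** **1. The plan's sample size and the quantity behind it.** Inputs from section 9.2: means 1.06 and 0.925 m/s, difference entered as 0.14; variance 0.03; two-sided 0.05; power 0.80; n = 2(Zα + Zpower)²σ²/Δ².
- With the plan's constant: 15.79 × 0.03 / 0.14² = 24.17.
- With unrounded normal quantiles: 15.698 × 0.03 / 0.0196 = 24.03.
- Attrition: 24 / (1 − 0.20) = 30; the plan's 24 × 1.2 = 28.8 is its 29, and its final figure is 30.

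The stated 24 reproduces, and it is based entirely on the level of gait speed.

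**2. Counting the outcomes.** Sections 1.1, 3, 4.1 and 8.1: 2 sway + 13 gait + 3 turn = 18. Section 9.4.2: sway in two planes (2), 13 gait parameters and 3 turn measures = 18, taking foot strike angle as heel strike angle and arm range of motion as the range of motion of the earlier lists. The parameters match; the quantity computed from them does not.

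**3. Does the Holm family show which was meant?** The first Holm step is 0.05/m.

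| Outcomes tested | m | 0.05/m |
|---|---|---|
| Levels only | 18 | 0.00278 |
| Stated in 9.4.2 | 20 | 0.0025 |
| Asymmetry and variability | 2 × 18 = 36 | 0.00139 |
| All three | 3 × 18 = 54 | 0.00093 |

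The stated 20 matches none of the three sets. Counting sway once gives 17, which does not match either.

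**4. Does the height normalisation show which was meant?** Section 9.4.1 divides speed and stride length by D² and multiplies cadence by D², where D² is height over mean height, a constant for each patient. For a coefficient of variation, SD(S/D²) / mean(S/D²) = SD(S) / mean(S): the factor cancels. It cancels in the same way in a ratio-type asymmetry index. The normalised labels SN, LN and CN appear in the 9.4.2 list, so they serve levels mainly. They would still affect an unscaled SD or an absolute left-right difference, and 9.4.2 does not say which form its indices take.

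**5. Can the named quantities be computed?** By the task description in 8.1, one SAW contains one 30-second stand and one 180-degree turn. A trial has two SAWs, or one if the participant cannot do both.
- Asymmetry: no left-right version is evident for antero-posterior or medio-lateral sway RMS or for a single turn (2 + 3 = 5 measures). Cadence and double support raise the same question.
- Variability across repeats for those five measures: two values per trial, or one. With one value there is no SD. With two normal values, the SD has relative standard error √(1 − 2/π) / √(2/π) = 0.603/0.798 = 0.756, about 76%.

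An index computed within a stand or within a turn could get round this, but the plan defines none.

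**The case against.** The strongest reply is that levels were plainly intended and one sentence is loosely worded. Much of this stands. The model sentence names no dependent variable, and the sentence before it describes what the software calculates without excluding the parameter values. Section 9.4.1 plans means and SDs of the gait parameters and normalises three of them for height, the 9.4.2 list carries those normalised labels, and section 9.2 uses mean speed. A reader might infer from 9.4.2 that Aim 1 tests a different endpoint from the declared one. The documents do not establish that; it is one reading, and the less likely one.

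A reader might also infer that the five sway and turn measures cannot be scored at all. That goes too far. Asymmetry and variability are undefined, so what the software can return for a stand or a turn cannot be known from the documents, and two SAWs per trial is the default. RMS sway is itself a measure of dispersion, so a simple contrast of level with variability does not fit it.

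These replies show what was probably meant. They do not supply the missing response variable, and the stated count of 20 does not support the intended reading either.

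**Conclusion.** The contradiction is real and concerns the primary analysis. Four sections define 18 parameter values; the one analysis section names asymmetry and variability for the same 18 and leaves the model's response unstated. The surrounding text favours levels, but the plan as written allows either analysis. The difficulty of computing the indices for five of the 18 measures is inferred from the task description, and it holds unless within-stand or within-turn indices are defined. The 76% figure assumes normal values.

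No loss of power can be attached to this point from the documents. They give no stride-level SD, no within-patient SD and no expected 60 Hz effect on variability or asymmetry. Any power comparison would rest on assumed inputs, and would also have to use the Holm threshold, not 0.05. The importance of the point lies in leaving the primary test undefined. It gives no reason to change the sample size, which already rests on a level.

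**What to change.** In section 9.4.2, state that the response for Aims 1.1 and 1.2 is the per-trial value of each parameter as defined in 1.1, 3 and 8.1: the mean over strides and SAW repeats for gait, the RMS per stand for sway, and the value per turn for turning, with sway and turn values averaged over repeats.

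Label asymmetry and variability as additional outcomes, give a formula for each, and list the parameters to which each applies. If the sponsor wants either as primary, add it to 1.1, 3 and 8.1. How they rank beyond that is the sponsor's choice.

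Replace the 20 in the Holm sentence with the count that results: 18 for levels only, more if other outcomes are declared primary.

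The cost is a few sentences, with no new data and no change in N. The downside is that asymmetry and variability lose any primary status unless they are declared as primary.

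### The Holm-Bonferroni count of 20 for Aim 1.1 matches no list in the plan (18 measures are named), and the plan does not say whether asymmetry and variability are among the tests it covers

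*Combined protocol and SAP*

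**What the plan says.** Section 9.4.2 of the combined protocol and SAP gives the multiplicity rule for Aim 1.1: "The Holm-Bonferroni method will be used to adjust for multiple comparisons for the 20 outcome measures".

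The measures are listed earlier in the same paragraph. The list opens with "postural sway (RMS AP & ML planes), cadence (CN), gait cycle duration, gait speed (SN), swing, double support", continues with midswing elevation, two foot angles, stance, step duration and stride length, and closes with "arm swing velocity, arm range of motion, turn angle, turn duration, and turn velocity". It is introduced by the statement that "the SWAY and TUG algorithms included in the SAW test will calculate asymmetry and variability for" these measures. The paragraph then moves to the mixed model comparing low and high frequency. It does not say whether the modelled outcome is the mean level of each measure, its asymmetry, its variability, or all three.

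The synopsis (section 1.1) lists the primary gait endpoints as parameters with units. Sway is given as "root mean square (RMS) sway in antero-posterior (AP) and medio-lateral (ML) planes", followed by 13 gait and 3 turning parameters. Asymmetry and variability do not appear there. Sections 3, 4.1 and 8.1 repeat the same parameters. None of these sections explains the figure of 20.

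**The concern.** The Holm count sets the significance threshold for every Aim 1.1 result, and it is the only multiplicity rule the plan states for the primary endpoints. Holm protects the 5% level only if the count is at least the number of tests actually run. Here the stated count matches no list, and the set of tests is not defined.

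The direction of the consequence depends on what is tested. With fewer than 20 tests the threshold is a little too strict and some power is lost. With more than 20 the 5% guarantee is gone. While the family stays open, the choice between mean, asymmetry and variability could also be made after the data are seen.

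**Working it through.** **Step 1: try to reproduce 20.**

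| Group | Section 9.4.2 | Synopsis |
|---|---|---|
| Sway, AP and ML | 2 | 2 |
| Gait and arm measures | 13 | 13 |
| Turning | 3 | 3 |
| Total | 18 | 18 |

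The 13 are cadence, cycle duration, speed, swing, double support, midswing elevation, foot (heel) strike angle, toe-off angle, stance, step duration, stride length, arm velocity and arm range of motion. Sway as a single item gives 17. Two statistics per measure give 2 × 18 = 36, and three give 3 × 18 = 54. No count stated in the plan gives 20.

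**Step 2: error when only the 18 means are tested but the count is 20.** Assume one frequency test per measure. The first threshold is 0.05/20 = 0.0025. If m of the 18 nulls are true, the first false rejection comes after at most 18 − m correct ones, so it faces a threshold of at most 0.05/(20 − (18 − m)) = 0.05/(m + 2). The error is then at most m × 0.05/(m + 2), which is largest at m = 18: 18 × 0.0025 = 0.045. Control holds, and 0.5 percentage points are unused. If the tests were independent, the error would be 1 − 0.9975^18 = 4.4%.

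**Step 3: power lost by using 20 instead of 18.** The inputs are n = 24 (section 9.2), a two-sided paired t-test with 23 degrees of freedom, and noncentrality d√24. The values d = 0.8 and d = 0.6 are assumed within-patient effects, not figures from the plan.

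| Holm count | First threshold | Power, d = 0.8 | Power, d = 0.6 |
|---|---|---|---|
| 20 | 0.00250 | 69.3% | 35.5% |
| 18 | 0.00278 | 70.7% | 36.9% |
| 17 | 0.00294 | 71.5% | 37.7% |

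Correcting 20 to 18 gains about 1.4 percentage points.

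**Step 4: error when asymmetry and variability are tested with the count at 20.** For k tests, the first-step bound when no measure truly differs is k × 0.0025. Under independence it is 1 − 0.9975^k. The partial rows assume that left/right asymmetry exists for about 10 of the 18 measures.

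| Tests run | k | Bound | If independent |
|---|---|---|---|
| Variability (18) + asymmetry (10) | 28 | 7.0% | 6.8% |
| Variability (18) + asymmetry (18) | 36 | 9.0% | 8.6% |
| Means + variability + asymmetry (10) | 46 | 11.5% | 10.9% |
| Means + variability + asymmetry (18) | 54 | 13.5% | 12.6% |

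**Step 5: overlap within the list.** Taking both as percentages of the gait cycle, swing = 100 − stance. The mixed model for one then returns the other's frequency effect with the sign reversed, the same standard error and the same p-value. Cadence is different. It is a reciprocal of step duration, and section 9.4.1 rescales it for height (C × D²) while the durations are not rescaled. Its test is close to those for step and cycle duration but not identical.

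**The case against.** The strongest reply is that 18 against 20 does no harm. If the synopsis parameters are the outcomes, the larger count is conservative and costs about one point of power. That stands. A reader might infer from the mismatch that the stated error control is wrong and that alpha is wasted as well. The documents do not support that pair of claims, because they belong to opposite readings: with 18 tests control holds and a little alpha is unused, while with more than 20 tests control is lost and nothing is wasted.

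Second, the plan says that asymmetry and variability will be calculated, not that each is a tested outcome, and the synopsis names neither. Asymmetry is also not obviously defined for sway, cadence or turning. That stands too. The 9.0% and 13.5% bounds are therefore upper scenarios and not a property of the plan as written. The outcomes are also correlated, so the actual error may lie below the bound. The gap that remains is that the paragraph does not exclude these tests, and even the narrower 28-test case exceeds 5%.

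Third, 20 may be an undocumented count. Sensors are worn on both wrists, and counting the two arm measures by side would give 18 + 2 = 20. No section says this, so it cannot be used to read the rule, but it means that 20 need not be a slip.

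Fourth, a reader might infer that overlapping outcomes invalidate the correction, or that swing, step duration and cycle duration must all be dropped. Neither follows. Holm is valid under any dependence, and only swing and stance give the same test. Removing the two durations as well would be a preference.

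**Conclusion.** The point holds as a mismatch and an undefined family, not as a demonstrated failure of error control. The count of 20 agrees with no list in the plan, and both lists give 18.

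On the reading closest to the synopsis (18 mean parameters, one frequency test each), family-wise error is at most 4.5% and the loss is about 1.4 points of first-step power. If asymmetry and variability are tested, the 5% guarantee fails, with bounds from 7.0% (28 tests) to 13.5% (54 tests). The text leaves this open and does not state it.

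The power figures rest on a paired t-test and assumed effects, in place of the planned mixed model over four contact pairs. They show the size of the change, not the trial's power. The error bounds describe the case where frequency affects none of the measures. The 28- and 46-test rows rest on the assumption of about 10 measures with asymmetry.

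The correction is worth making because this figure sets the significance threshold for Aim 1.1 and the change needs only wording.

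**What to change.** In section 9.4.2, define the Aim 1.1 confirmatory family as the named mean parameters in the synopsis, and set the Holm count to that number. That is 18, or 17 if swing % is dropped as the complement of stance %, which loses no information. If the arm measures are meant to be tested by side, say so and count them that way.

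State that asymmetry and variability are exploratory and reported without significance claims. Otherwise, list each one to be tested and include it in the count. State also whether the Aim 1.2 levodopa tests, for which no adjustment is given, belong to this family. Dropping step duration and cycle duration as well is optional.

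The change is to SAP wording only, with no effect on data collection. The downside is small: asymmetry and variability lose confirmatory status, or, if they are counted, the first threshold tightens to between 0.05/46 = 0.0011 and 0.05/54 = 0.0009 when they are tested alongside the 18 means.

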9 STATISTICAL CONSIDERATIONS

9.1 STATISTICAL HYPOTHESES

Aim 1. Our preliminary study established that gait and rest tremor are important factors to determine whether patients benefit from 60Hz stimulation or high frequency stimulation (38). However, the degree to which stimulation parameters affect gait parameters is not well established. In Aim 1, we will test the *hypothesis* that certain gait parameters are differentially affected between 60Hz and high frequency STN-DBS at various electrode contact configurations. In addition, in our preliminary analysis, we observed a modest reduction in dopaminergic medications in patients on 60Hz stimulation (12). Hence, we will also test the *hypothesis* that for some patients, the addition of levodopa in combination with 60Hz stimulation produces a synergistic improvement in certain gait domains.

Aim 2. Our preliminary data suggested that there is a link between the patient's baseline motor symptomatology measured by the MDS-UPDRS III ratings and the best stimulation frequency (60 Hz or HFS) chosen for the patient based on intensive clinical evaluations, which remained unchanged for an average of 12 months. In Aim 2, we test the *hypothesis* that a subject's gait kinematics on 60Hz stimulation can be predicted with statistically significant accuracy using gait measurements on high frequency stimulation. In addition, we will test the *hypothesis* that the best stimulation frequency (60Hz or HFS stimulation), which yields improvement among various gait parameters, can be predicted using objective sensor data collected at baseline. We define baseline motor performance as the severity of motor symptoms in the levodopa OFF and ON state without stimulation. In the remainder of this proposal, for simplicity we refer to 60 Hz stimulation and high frequency stimulation (130-180Hz) as low frequency (LFS) and high frequency (HFS), respectively.

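### Holm-Bonferroni is written only for Aim 1.1; Aim 1.2, also primary on the same gait parameters, has no stated multiplicity rule and no named term for its synergy hypothesis

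*Combined protocol and SAP*

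**What the plan says.** - **Aim 1.1 (section 9.4.2).** Linear mixed models compare high and low frequency over the contact pairs in the levodopa-OFF state. The paragraph ends: "The Holm-Bonferroni method will be used to adjust for multiple comparisons for the 20 outcome measures". No other section gives a multiplicity rule; the general approach in 9.4.1 has none.
- **Aim 1.2 (section 9.4.2).** The next paragraph is a single sentence: "we will include the data for levodopa-ON and add a binary variable for levodopa (on or off) to the LMMRM from Aim1.1". It states no alpha, contrast, interaction term or adjustment.
- **Status of Aim 1.2.** The synopsis (1.1) and the objectives table (section 3) place it with Aim 1.1, under the primary objectives and with the same gait endpoints. Section 9.4.9 lists no exploratory analyses.
- **Hypothesis behind Aim 1.2 (section 9.1).** For some patients, levodopa combined with 60 Hz stimulation "produces a synergistic improvement in certain gait domains". No domain is named.
- **Error level.** The only alpha in the plan is in the sample-size section (9.2): "with a power of 0.80 and level of significance of 0.05".

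**The concern.** A hypothesis that succeeds if any of some 20 gait parameters shows synergy is the kind of claim a family-wise procedure exists for. The plan accepts this for its first primary question and assigns no rule to the second, which uses the same patients and outcomes. An analyst following the text literally would report each Aim 1.2 parameter at its own 5% level. An isolated synergy result could then be put forward as confirmed when chance alone would often produce one. Section 2.1 says the study is meant to lead to a randomised trial, so such a result could influence that trial's design.

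There is a second gap. A binary levodopa variable added to the model is, as written, a main effect. It asks whether gait differs on and off levodopa, averaged over frequency. Synergy between levodopa and 60 Hz is a frequency-by-levodopa interaction. A multiplicity rule cannot be fully stated until the plan says which term it applies to.

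**Working it through.** **Inputs from the plan.** Alpha 0.05, two-sided (Z = 1.96), power 0.80, difference 0.14, variance 0.03, n = 24 before attrition (all 9.2). The outcome count is stated as 20 in 9.4.2. The measures listed there come to 18 when antero-posterior and medio-lateral sway are counted separately, so both counts are carried.

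**Assumptions.** One two-sided 5% test per outcome in Aim 1.2; no true effect on the tested term for any outcome; test statistics jointly normal with one common correlation. The plan gives no correlation, so a range is shown.

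**1. The plan's own figure.** 15.79 × 0.03 / 0.14² = 24.17, which agrees with the stated 24. The standardised difference is 0.14 / √0.03 = 0.81, close to the stated 0.8. This calculation uses an unadjusted 0.05. The plan states no family-wise error for Aim 1.2, so there is no figure of that kind to reproduce.

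**2. Independent tests.** P(at least one false positive) = 1 − 0.95^m.
- m = 18: 1 − 0.95^18 = 60.3%
- m = 20: 1 − 0.95^20 = 64.2%

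**3. Correlated tests.** By simulation, 100,000 draws per case:

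| Assumed correlation | 18 outcomes, unadjusted | 20 outcomes, unadjusted | 20 outcomes, Holm |
|---|---|---|---|
| 0 | 60% | 64% | 4.9% |
| 0.3 | 51% | 54% | 4.3% |
| 0.5 | 40% | 42% | 3.5% |
| 0.7 | 28% | 29% | 2.4% |
| 0.9 | 15% | 16% | 1.2% |

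**4. What Holm per term guarantees.** Within one term, family-wise error is at most 5% under any correlation. With two terms (interaction and levodopa main effect), each with its own Holm family, the bound is 0.05 + 0.05 = 10%; if independent it is 1 − 0.95² = 9.75%. Pooling both terms in one family of 2 × 20 = 40 tests restores 5% overall, with a first-step threshold of 0.05 / 40 = 0.00125.

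**5. Cost in power.** Holm's first step uses 0.05 / 18 = 0.0028 or 0.05 / 20 = 0.0025. For a paired t-test with 24 patients and an assumed standardised effect of 0.8 (noncentral t, noncentrality 0.8 × √24 = 3.92), power is 96% at 0.05, 71% at 0.05 / 18 and 69% at 0.05 / 20.

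**The case against.** **The plan is silent; it does not prescribe unadjusted tests.** A reader might infer that the plan sets 5% for each Aim 1.2 test. It does not say so. Aim 1.2 extends the Aim 1.1 model on the same outcomes, so Holm may have been meant to carry over. This stands as a limit on the point. But the sentence carries over the model, whereas Holm is a rule for p-values. If Aim 1.2 adds a tested term per outcome, the family could be 20, 40 or two separate sets, and nothing says which.

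**A levodopa finding is not shown to be a chance finding.** A reader might infer that any levodopa effect on one or two parameters would probably be spurious. The documents do not support that. All participants are on levodopa (5.1) and receive 1.5 times their usual dose, up to 300 mg, to secure the ON state (4.1), so real main effects are plausible. The error rates above suit the interaction, which the plan does not write down.

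**Independence is unrealistic.** Stance and swing percentages are complementary; cadence, step duration and cycle duration are closely tied. The correlated rows are the more relevant ones. Even at 0.9 the rate is about three times nominal.

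**Aim 2.** Section 9.1 says gait on 60 Hz "can be predicted with statistically significant accuracy using gait measurements on high frequency stimulation", and a reader might extend the point to Aim 2. The analysis text for Aims 2.1 and 2.2 specifies cross-validation, benchmark models and bootstrap intervals, with no significance test per parameter. The point does not extend there.

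**Power.** The 0.8 paired effect is borrowed from a two-group calculation. On that two-group formula, power at n = 24 falls from 80% to about 41% to 42% at Holm's first step. Neither figure describes an interaction in the mixed model, so the cost is real and not well known. Separate families for separate questions, in a study of 30 patients, is also a defensible choice; it needs only to be stated.

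**Conclusion.** The point holds as a gap in scope and specification. The only multiplicity rule is attached to the levodopa-OFF frequency comparison; a second primary sub-aim on the same parameters, with an any-domain hypothesis, has no rule and no stated interaction term. Read literally, and with no true interaction on any outcome, the family-wise error for Aim 1.2 lies between about 15% and 64%, with 40% to 42% at a correlation of 0.5. The range rests on one test per outcome, 18 to 20 outcomes and an assumed common correlation. It applies to the interaction, not to the levodopa main effect. It should be put right before analysis.

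**What to change.** In 9.4.2, Aim 1.2:

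1. Name the tested term: the frequency-by-levodopa interaction for the synergy hypothesis, with the levodopa main effect reported alongside.
2. State that Holm-Bonferroni is applied across all gait parameters for each tested term, as in Aim 1.1, and list the parameters so that the family size (18 or 20) is fixed.
3. Say whether the two terms form separate families (5% per term, at most 10% over both) or one pooled family (5% overall).

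The cost is a few sentences and no new data. The downside is the stricter threshold per parameter: under the assumed paired effect of 0.8 at n = 24, a drop from about 96% to about 70% power at the first step. Pooling the terms would cost more.
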